4.2 SCIENTIFIC RATIONALE FOR STUDY DESIGN

The methodology of a dose-ranging, randomized, parallel group, split-face, single-blind, mock-controlled study offers several advantages.

A dose-ranging study design is implemented as the safety of LED-RL phototherapy in a surgical wound model may differ from the safety in normal skin. For example, higher fluences determined to be safe in normal skin may potentially cause problems in post-surgical/scarred skin, such as dehiscence. Thus, the MTD established in our Phase I studies serves as the upper limit of treatment dose in this study.

The split-face study design allows each subject to serve as his or her own control, allowing for a within-subject comparison of clinical efficacy between the treated side and mock-treated side. That is, any observed improvements in scar characteristics can be attributed to the treatment. The split-face design also eliminates the need to consider inter-individual differences in wound healing as a confounding factor when comparing different treatment arms. It is important to note that in the prospective evaluation of scar reduction therapy, it is assumed that if left untreated, the wounds on the treated side and untreated side would heal with identical scars. Since wound healing and scar

formation are influenced by many variables, the selection of a self-controlled study design is favored to allow detection of true treatment effects.

There are no known problems associated with the control (sham irradiation), since the mock device is designed to simulate the treatment device without actually producing light.

The mini-facelift with periauricular incisions is an ideal model for studying wound healing and skin fibrosis because: patients are motivated to have the best wound healing outcomes and aesthetic results (i.e., minimal or imperceptible scarring), hence will likely be compliant with therapy and have a low attrition rate; patients are usually healthy in order to be suitable candidates for the surgery; and the periauricular skin is at risk of pathological scar development, yet has low skin tension and robust blood circulation to allow for optimal wound healing.

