8.3.3 CLASSIFICATION OF AN ADVERSE EVENT

8.3.3.1 SEVERITY OF EVENT

For AEs not included in the protocol defined grading system, the following guidelines will be used to describe severity.

- **Mild** Events require minimal or no treatment and do not interfere with the participant's daily activities.
- **Moderate** Events result in a low level of inconvenience or concern with the therapeutic measures. Moderate events may cause some interference with functioning.
- Severe Events interrupt a participant's usual daily activity and may require systemic drug therapy or other treatment. Severe events are usually potentially life-threatening or incapacitating. Of note, the term "severe" does not necessarily equate to "serious".

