8.3.4 TIME PERIOD AND FREQUENCY FOR EVENT ASSESSMENT AND FOLLOW-UP

The occurrence of an AE or SAE may come to the attention of study personnel during study visits and interviews of a study participant presenting for medical care, or upon review by a study monitor.

All AEs including local and systemic reactions not meeting the criteria for SAEs will be captured on the appropriate CRF. Information to be collected includes event description, time of onset, clinician's assessment of severity, relationship to the study intervention (assessed only by those with the training and authority to make a diagnosis), and time of resolution/stabilization of the event. All AEs occurring while on study must be documented appropriately regardless of relationship. All AEs will be followed to adequate resolution.

Any medical condition that is present at the time that the participant is screened will be considered as baseline and not reported as an AE. However, if the study participant's condition deteriorates at any time during the study, it will be recorded as an AE.

Changes in the severity of an AE will be documented to allow an assessment of the duration of the event at each level of severity to be performed. AEs characterized as intermittent require documentation of onset and duration of each episode.

The investigators will record all reportable events with start dates occurring any time after informed consent is obtained until 7 (for non-serious AEs) or 30 days (for SAEs) after the last day of study participation. At each study visit, the investigator will inquire about the occurrence of AE/SAEs since the last visit. Events will be followed for outcome information until resolution or stabilization.

[figure not shown]

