9.4.4 SAFETY ANALYSES

AEs, SAEs, and UPs will be recorded and reported as described in the protocol. The information documented about each event or problem includes onset, duration, severity, relationship to the study intervention, and outcome. Summary statistics of safety data will be presented as number of subjects who experienced AEs in each treatment group and a breakdown of the event types. AEs will be coded according to the terminology in the Medical Dictionary for Regulatory Activities (MeDRA). AEs leading to premature discontinuation from the study and serious treatment-emergent AEs will also be presented.

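### Section 9.4.4 plans no AE summary by severity, relationship, duration or number of episodes, and does not say what the event-type breakdown counts

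*Combined protocol and SAP*

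**What the plan says.** Section 9.4.4 first lists what is recorded: "The information documented about each event or problem includes onset, duration, severity, relationship to the study intervention, and outcome". It then names the summary statistics: the "number of subjects who experienced AEs in each treatment group and a breakdown of the event types". Two further displays follow: "AEs leading to premature discontinuation from the study and serious treatment-emergent AEs will also be presented". The unit of the event-type breakdown, subjects or events, is not given.

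Section 8.3.4 states why some of this detail is collected: "Changes in the severity of an AE will be documented to allow an assessment of the duration of the event at each level of severity". It adds that "AEs characterized as intermittent require documentation of onset and duration of each episode".

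The design rationale in 4.2 rests partly on safety: "A dose-ranging study design is implemented as the safety of LED-RL phototherapy in a surgical wound model may differ" from that in normal skin. Section 4.3 accepts the risk of blistering on the expectation that it will be mild and leave no lasting effect. Section 10.2 says that opening the highest dose to all skin types is meant to generate more safety data there.

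Elsewhere in Section 9, 9.4.8 provides listings of individual data by measure and time point, and 9.4.9 plans no exploratory analyses.

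**The concern.** The plan collects severity, relationship, duration and separate episodes, and in one place says what the severity and duration data are for. The analysis section then names no display that uses any of them.

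This matters because tolerability across three doses is part of what the trial is meant to learn. The expectation behind accepting blistering in 4.3 concerns how severe blisters are and whether they resolve. A count of subjects with a blister, by dose, cannot confirm or contradict that. A report that follows 9.4.4 exactly could show similar numbers affected at each dose while saying nothing about whether reactions at one dose were worse or lasted longer.

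**Working it through.** **Inputs.** Nine evaluable subjects per arm and 10% dropout (9.2); three sessions a week for three weeks (1.3, 6.1.2); severity graded mild, moderate or severe (8.3.3.1); displays from 9.4.4; collection from 8.3.4. Section 9.4.4 gives no figure of its own, and the documents give no AE rate by arm for this trial.

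**Arm size and exposure.** 9 / (1 − 0.10) = 10 per arm, which reproduces the plan's figure. Sessions per subject: 3 × 3 = 9, so at most 10 × 9 = 90 per arm.

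**Collected against displayed.**

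| Information | Collected | Display in 9.4.4 |
|---|---|---|
| Any AE, per subject | 8.3.4, 8.3.5 | Yes, by dose group |
| Event type | 8.3.4 | Yes, counting unit not stated |
| Serious AE | 8.3.2, 8.3.6 | Yes |
| AE leading to leaving the study | 7.2 | Yes |
| Severity grade | 8.3.3.1, 8.3.4 | None |
| Relationship to intervention | 8.3.3.2 | None |
| Duration, including by severity level | 8.3.4 | None |
| Number of episodes | 8.3.4 | Only if the breakdown counts events |

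The serious-AE display does not stand in for severity, because 8.3.3.1 states that severe and serious are different things. The discontinuation display does not capture everyone who stops treatment because of a reaction. Section 7.1 separates stopping LED-RL from leaving the study, and 9.4.4 covers only the latter.

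**Severity and duration.** Take two hypothetical arms, each with 4 of 10 subjects having one non-serious reaction of the same type. In one arm all four are mild and brief; in the other they are moderate or severe and long-lasting. Nobody leaves the study. Every display in 9.4.4 is then identical: 4 of 10, same event type, no serious AEs, no discontinuations. This holds whether the breakdown counts subjects or events, and at any event rate.

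**Recurrence, if the breakdown counts subjects.** With k subjects affected and at most one episode per session, episodes can run from k to 9k. For k = 4 that is 4 to 36; for k = 6 it is 6 to 54. These are bounds, not expectations.

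**How much recurrence is likely to be hidden.** The only rate in the documents is in 8.3.5: transient erythema and warmth in 10% of participants in other studies. As an assumption, read that as 10% per subject over nine independent sessions:

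- Per-session risk: p = 1 − 0.9^(1/9) = 0.0116. Expected subjects affected: 10 × 0.10 = 1.0. Expected events: 90 × 0.0116 = 1.05.
- Triple the risk: p = 0.0349. Expected subjects: 10 × (1 − 0.9651^9) = 2.7. Expected events: 90 × 0.0349 = 3.1.

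At rates of this order the subject count rises 2.7-fold against 3-fold for events, so it loses little about recurrence.

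**The case against.** Safety in this trial does not rest on one table. The Independent Safety Monitor reviews AEs as they occur and assesses safety by arm (10.1.6), all AEs go to monthly meetings (8.3.5), and individual data are listed (9.4.8). With 30 subjects, case-by-case reading is practical, and 8.3.4 does not say that its assessment of duration must be a Section 9 table. A subject with repeated severe reactions would probably surface in the serious-AE or discontinuation display, since 8.3.3.1 describes severe events as usually potentially life-threatening or incapacitating and 7.2 lets the investigator withdraw such a subject. Much of this stands: participants are monitored, and extreme differences between doses would be likely to show. It does not supply a summary by dose, and it does not reach moderate, persistent or severe-but-not-serious reactions in subjects who stay in the study.

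Three stronger readings are tempting, and the documents do not support them.

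- A reader might infer that each subject is counted once per event type. The text does not say so. The headline count is by subject, but the unit of the breakdown is left open.
- A reader might infer that over nine sessions the subject count saturates, so that arms of very different tolerability look alike. That needs a high per-session risk. At an assumed 20%, 10 × (1 − 0.8^9) = 8.7 of 10 subjects would be affected. The documents' only figure is 10% of participants, and it concerns transient effects that 8.3.1 does not count as AEs unless they persist or are serious.
- A reader might infer a loss of statistical power. Section 9.4.4 plans no safety test, so power is not at issue.

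**Conclusion.** The gap is real and limited. None of the displays named in 9.4.4 uses severity, relationship or duration, and the breakdown has no stated counting unit. Followed exactly, the plan cannot separate the three doses on severity short of serious, or on persistence; this conclusion needs no assumption about event rates. Recurrence is hidden only if the breakdown counts subjects, and to an important degree only if reactions are frequent. The nine-fold range is an upper bound that assumes at most one episode per session.

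No estimate is biased, and the efficacy analysis is untouched. What is lost is the dose-by-dose description of tolerability to which 4.2, 4.3 and 8.3.4 all point. The change is worth making before safety data are tabulated.

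**What to change.** In 9.4.4, keep the existing displays and add the following, by dose group and descriptively:

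- subjects by worst severity within each event type, and by relationship to the intervention;
- the number of events beside the number of subjects for each event type, with the counting rule stated, including when a recurrence is a new event;
- duration by severity level, as 8.3.4 provides for.

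Per-session rates with intervals clustered by subject are not needed. With 10 subjects per arm such intervals would be unreliable, and a reaction that lasts into the next session, about two days later, has no clear session to belong to.

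The cost is a few extra tables from data already on the case report forms, with no new collection and no change to sample size. With 10 per arm the tables describe and do not test.

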9.4.5 BASELINE DESCRIPTIVE STATISTICS

Descriptives of relevant subject characteristics (age, gender, race, and ethnicity) of the entire study population (i.e., intent-to-treat population) will be tabulated by treatment group. Continuous variables will be presented as median and range. Categorical variables will be presented as proportions. Significance tests will not be applied.

9.4.6 PLANNED INTERIM ANALYSES

N/A

9.4.7 SUB-GROUP ANALYSES

To determine if any differential effects of LED-RL are associated with demographics (race, ethnicity, age, and gender), a linear regression or robust linear regression with adjustment for treatment group effect on pliability will be performed.

9.4.8 TABULATION OF INDIVIDUAL PARTICIPANT DATA

Individual participant data will be listed by measure and time point for raw data analyses.

9.4.9 EXPLORATORY ANALYSES

N/A

10 SUPPORTING DOCUMENTATION AND OPERATIONAL CONSIDERATIONS

10.1 REGULATORY, ETHICAL, AND STUDY OVERSIGHT CONSIDERATIONS

10.1.1 INFORMED CONSENT PROCESS

10.1.1.1 CONSENT/ASSENT AND OTHER INFORMATIONAL DOCUMENTS PROVIDED TO PARTICIPANTS

Consent forms describing in detail the study intervention, study procedures, and risks are given to the participant and written documentation of informed consent is required prior to starting intervention/administering study intervention. The following consent materials are submitted with this protocol:

- LED-Red Light Phototherapy for Skin Scarring Prevention Informed Consent for Research Study
- Consent to Invasive Procedure (Optional Skin Biopsy)
- Research Study Summary for Potential Participants

10.1.1.2 CONSENT PROCEDURES AND DOCUMENTATION

Informed consent is a process that is initiated prior to the individual's agreeing to participate in the study and continues throughout the individual's study participation. Consent forms will be IRB-approved and the participant will be asked to read and review the document. The investigator will explain the research study to the participant and answer any questions that may arise. A verbal explanation will be provided in terms suited to the participant's comprehension of the purposes, procedures, and potential risks of the study and of their rights as research participants.

will have the opportunity to carefully review the written consent form and ask questions prior to signing. The participants should have the opportunity to discuss the study with their family or surrogates or think about it prior to agreeing to participate. The participant will sign the informed consent document prior to any procedures being done specifically for the study. Participants must be informed that participation is voluntary and that they may withdraw from the study at any time, without prejudice. A copy of the informed consent document will be given to the participants for their records. The informed consent process will be conducted and documented in the source document (including the date), and the form signed, before the participant undergoes any study-specific procedures. The rights and welfare of the participants will be protected by emphasizing to them that the quality of their medical care will not be adversely affected if they decline to participate in this study.

10.1.2 STUDY DISCONTINUATION AND CLOSURE

This study may be temporarily suspended or prematurely terminated if there is sufficient reasonable cause. Written notification, documenting the reason for study suspension or termination, will be provided by the suspending or terminating party to the NIH. If the study is prematurely terminated or suspended, the PI will promptly inform study participants, the IRB, and sponsor and will provide the reason(s) for the termination or suspension. Study participants will be contacted, as applicable, and be informed of changes to study visit schedule.

Circumstances that may warrant termination or suspension include, but are not limited to:

- Determination of unexpected, significant, or unacceptable risk to participants
- Demonstration of efficacy that would warrant stopping
- Insufficient compliance to protocol requirements
- Data that are not sufficiently complete and/or evaluable
- Determination that the primary endpoint has been met
- Determination of futility

Study may resume once concerns about safety, protocol compliance, and data quality are addressed, and satisfy the sponsor, IRB and/or FDA.

10.1.3 CONFIDENTIALITY AND PRIVACY

Participant confidentiality and privacy is strictly held in trust by the participating investigators, their staff, and the sponsors and their interventions. This confidentiality is extended to cover testing of biological samples and genetic tests in addition to the clinical information relating to participants. Therefore, the study protocol, documentation, data, and all other information generated will be held in strict confidence. No information concerning the study or the data will be released to any unauthorized third party without prior written approval of the sponsor.

All research activities will be conducted in as private a setting as possible.

The study monitor, other authorized representatives of the sponsor, representatives of the IRB, or regulatory agencies may inspect all documents and records required to be maintained by the investigator, including but not limited to, medical records (office, clinic, or hospital) and pharmacy records for the participants in this study. The clinical study site will permit access to such records.

The study participant's contact information will be securely stored at each clinical site for internal use during the study. At the end of the study, all records will continue to be kept in a secure location for as long a period as dictated by the reviewing IRB, Institutional policies, or sponsor requirements.

Study participant research data, which is for purposes of statistical analysis and scientific reporting, will be managed and protected in accordance with SUNY Downstate Medical Center Human Research Protections Program. This will not include the participant's contact or identifying information. Rather, individual participants and their research data will be identified by a unique study identification number. Written study subject individual or aggregate data from the study will be secured in a locked cabinet, in a locked room. Computerized data will be stored on the HIPAA-compliant SUNY Downstate Department of Dermatology desktop computers that are connected to the SUNY Downstate Medical Center's secure network behind a firewall, complete with 128-bit data encryption. Storage of any PHI on a laptop or portable device (e.g., external drive, flash drive, CD/DVD, USB drive or similar) will be encrypted and used only for temporary storage. In addition to being encrypted, removable storage devices will be stored in a locked cabinet or drawer when not in use.

Certificate of Confidentiality

To further protect the privacy of study participants, a Certificate of Confidentiality will be issued by the NIH. This certificate protects identifiable research information from forced disclosure. It allows the investigator and others who have access to research records to refuse to disclose identifying information on research participation in any civil, criminal, administrative, legislative, or other proceeding, whether at the federal, state, or local level. By protecting researchers and institutions from being compelled to disclose information that would identify research participants, Certificates of Confidentiality help achieve the research objectives and promote participation in studies by helping assure confidentiality and privacy to participants.

10.1.4 FUTURE USE OF STORED SPECIMENS AND DATA

Biological samples and data collected for this study will not be stored for future research after the study is completed.

10.1.6 SAFETY OVERSIGHT

Safety oversight will be under the direction of an Independent Safety Monitor (ISM) with the appropriate expertise. For this study, the ISM is [name], the Director of Clinical Research in the Department of Dermatology at SUNY Downstate. The ISM is independent from the study conduct and free of conflict of interest. The ISM will meet at least semiannually to assess safety and efficacy data on each arm of the study. The primary responsibility of the ISM is to provide independent safety monitoring in a timely fashion, including by review of AEs, immediately after they occur or are reported, with follow-up through resolution. The ISM will provide her input to the PI and study sponsor.

For this study, monitoring will be performed on a quarterly basis by the following entities:

- a. PI: [name], MS
- b. SUNY Downstate IRB
- c. Independent Safety Monitor: [name]
- d. Designated Medical Monitor: [name], PhD
- e. SUNY Downstate Department of Dermatology Clinical Research Faculty Committee: [name], PhD; [name]; [name]

10.1.7 CLINICAL MONITORING

Clinical site monitoring is conducted to ensure that the rights and well-being of trial participants are protected, that the reported trial data are accurate, complete, and verifiable, and that the conduct of the trial is in compliance with the currently approved protocol/amendment(s), with ICH GCP, and with applicable regulatory requirement(s).

- Monitoring for this study will be performed by the designated ISM. Monitoring will be on-site throughout the study and includes targeted data verification of endpoint, safety and other key data variables.
- Each clinical site will perform internal quality management of study conduct, data collection, documentation and completion.

10.1.8 QUALITY ASSURANCE AND QUALITY CONTROL

Each clinical site will perform internal quality management of study conduct, data and biological specimen collection, documentation and completion.

Quality control (QC) procedures will be implemented beginning with the data entry system and data QC checks that will be run on the database will be generated. Any missing data or data anomalies will be communicated to the site(s) for clarification/resolution.

Following written Standard Operating Procedures (SOPs), the monitors will verify that the clinical trial is conducted and data are generated and biological specimens are collected, documented (recorded), and reported in compliance with the protocol, ICH GCP, and applicable regulatory requirements (e.g., Good Laboratory Practices (GLP), Good Manufacturing Practices (GMP)).

The investigational site will provide direct access to all trial related sites, source data/documents, and reports for the purpose of monitoring and auditing by the sponsor, and inspection by local and regulatory authorities.

